- Official Title: Ultrasound-based Imaging to Detect Early Changes of Hard and Soft Tissue Around Immediately Placed Implants With or Without Soft Tissue Augmentation
- NCT Number: NCT05330702
- Document Date: 10/14/2024

Objective: The objective of this study is to compare and evaluate the stability of the implant body's survival rate over a period of 6 months using three different methods of immediate implant placement along with either soft tissue grafting (Connective Tissue Graft, Volume-Stable Collagen Matrix) or no soft tissue grafting.

Design: This study is a randomized clinical trial (*ClinicalTrials.gov identifier - NCT05330702*). The study population consists of adults aged 18-95 years old who are seeking care at the University of Iowa, College of Dentistry and Dental Clinics. Eligibility for the study included needed a tooth extraction and immediate implant placement at a location with the maxillary esthetic zone (first premolar to first premolar).

Methods: Immediately after tooth extraction, consented subjects underwent immediate implant placement and were randomized to either 2 groups of soft tissue grafting (connective tissue graft, volume-stable collagen matrix) or no soft tissue grafting. Participants have a 6-month follow-up visit after placement of the dental implant.

Statistical Analysis Plan: Values will be expressed as mean and standard deviation for continuous variables, such as linear measurements measured in mm, or absolute frequency and percentages for categorical variables. The normality will be assessed by means of a Kolmogorov-Smirnov test. The analysis of variance test or the Kruskal-Wallis's test with post-hoc analysis will be used to compare between three groups. Simple linear regression (univariate) analysis or analysis of covariance test will be employed to analyze the factors independently associated with peri-implant parameters. A two-tailed value of $P < 0.05$ is considered a significant level. Statistical analyses will be performed by the SPSS Statistical Software (IBM, version 28.0).

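### Does it matter that the three-arm comparison names no effect measure or confidence interval, and does not say how ANOVA or Kruskal-Wallis is chosen?

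*Combined protocol and SAP*

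**What the plan says.** The Statistical Analysis Plan section is one short paragraph. Four of its statements bear on this point, and a fifth sets the significance level.

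- Summaries: "Values will be expressed as mean and standard deviation for continuous variables, such as linear measurements measured in mm".
- Distribution check: "The normality will be assessed by means of a Kolmogorov-Smirnov test".
- Arm comparison, in the next sentence: "The analysis of variance test or the Kruskal-Wallis's test with post-hoc analysis will be used to compare between three groups".
- Covariates: "Simple linear regression (univariate) analysis or analysis of covariance test will be employed to analyze the factors independently associated with peri-implant parameters".
- Significance: "A two-tailed value of $P < 0.05$ is considered a significant level".

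No sentence names a mean difference, median, Hodges-Lehmann shift or confidence interval. None says outright that the normality result selects the test, which values are checked (each arm, pooled data or residuals), or whether the Kolmogorov-Smirnov test is corrected for an estimated mean and SD. The post-hoc procedure has no name. Nothing at this point is marked as redacted.

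This note covers measurements in mm. The implant survival rate in the Objective is a separate matter.

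**The concern.** The trial compares two soft tissue grafts with no graft, so the clinical question is how many millimetres separate the arms. The plan commits only to a P value. Three things look wrong.

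1. In a small trial, P above 0.05 does not show that grafting makes no difference. Without an interval, the reader cannot see which differences remain possible.
2. Means and SDs are fixed for every continuous variable. If the data are skewed and Kruskal-Wallis is used, a rank-based P value is printed beside summaries that may not show the difference it detects.
3. With the selection rule unstated, two analysts who both follow the plan could check normality differently, run different tests and reach different conclusions.

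At stake would be how well the results can be interpreted and, through the third point, whether they can be reproduced.

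**Working it through.** **Inputs.** From the document: three arms, two-tailed 0.05, and the two candidate tests. The document gives no sample size, SD, effect size or degree of skewness, so every figure below is illustrative. Assumptions: equal arms of 10 to 30, with two arms shifted relative to the third where an effect is assumed. The distributions are, in order, normal, lognormal (sigma 0.5), exponential and lognormal (sigma 1). There is no figure in the plan to reproduce.

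**Step 1: are the tests valid?** Six forms of the check were simulated: any single arm, pooled data or residuals, each with or without the Lilliefors correction, all at P < 0.05. Type I error of the check-then-test procedure was 0.035 to 0.058 across all forms and arm sizes. Power was never more than 0.003 below ANOVA. With the Lilliefors-corrected check on residuals at 15 per arm and a raw shift of 0.8, power was 58/97/77/58%. ANOVA alone gave 58/94/61/24% and Kruskal-Wallis alone 55/97/77/58%. So the two-test structure is close to the better test in every case.

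**Step 2: what is lost in the ANOVA branch?** The pairwise 95% half-width in SD units is t(0.975, 3n−3) × √(2/n):

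| n per arm | Half-width (SD) |
|---|---|
| 10 | 0.92 |
| 15 | 0.74 |
| 20 | 0.63 |
| 30 | 0.51 |

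These widths describe the imprecision of small trials, which the omission does not cause. Given means, SDs and n, a reader can compute the same interval, so what is lost is convenience.

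**Step 3: what is lost in the Kruskal-Wallis branch?** The question is how often a significant Kruskal-Wallis result comes with no Tukey interval, derived from the means and SDs, that excludes zero. The scale of the shift matters. A raw shift of 0.8 is a different standardised effect in each distribution:

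- lognormal 0.5: SD = √[(e^0.25 − 1)e^0.25] = 0.604, and 0.8/0.604 = 1.32 SD;
- exponential: SD = 1, so 0.8 SD;
- lognormal 1: SD = √[(e − 1)e] = 2.161, and 0.8/2.161 = 0.37 SD.

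At 15 per arm:

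| | Lognormal 0.5 | Exponential | Lognormal 1 |
|---|---|---|---|
| Raw shift 0.8, range over six checks | 6–25% | 25–45% | 59–82% |
| Common shift 0.8 SD, range over six checks | 24–45% | 26–47% | 26–47% |

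The apparent rise with skewness in the first row comes from unequal effect sizes. On a common scale the three skewed cases are alike, and with the Lilliefors-corrected residual check all three are about 24–26%. For normal data the figure is 7–12%.

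**Step 4: how often would analysts disagree?** For two of the six checks chosen at random, at 15 per arm:

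- No effect: 0.2/1.4/1.8/1.5% of trials reach different overall conclusions.
- Raw shift of 0.8: 0.7/1.8/8.9/9.9%.
- Same raw shift, both checks Lilliefors-corrected: 1.1/1.1/2.5/0.7%.

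The larger values need strong skew and an uncorrected check in the mix. Their ordering across distributions is confounded by the unequal standardised shifts described in step 3.

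**The case for a change.** The best case for a change is that it would be cheap. Pairwise differences with intervals need no new data, and a trial report that gives only P values serves readers poorly. Software may print intervals, but the plan does not commit to publishing them. The covariate sentence does not clearly fill the gap either: it is aimed at "analysis of covariance test will be employed to analyze the factors independently associated with peri-implant parameters", and although treatment arm is not excluded as a factor, the text does not name it as one.

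All of this is fair as advice on reporting. Three things limit it.

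- The selection rule is the plain reading of two adjacent sentences, and the general 0.05 level can serve as its threshold.
- Matching the interval to the rank test does not remove the mismatch. With Bonferroni-adjusted Hodges-Lehmann intervals, 14% of significant Kruskal-Wallis results in the lognormal 1 case (15 per arm, raw shift 0.8) still have no interval excluding zero, because those intervals come from pairwise Mann-Whitney tests and not from Kruskal-Wallis itself. A Hodges-Lehmann shift also reads as a difference in mm only if the arms have similar shapes.
- The Methods use the past tense, "consented subjects underwent immediate implant placement". If outcome data have already been seen, a rule added now would be a declared clarification without the value of pre-specification.

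**Conclusion.** The omissions are real, but no change to the plan is called for. Followed as written, the plan gives tests with type I error of at most about 0.058 in the settings simulated and no meaningful loss of power against ANOVA. It also promises summaries from which mean differences can be derived after ANOVA. The effect measure, the post-hoc procedure and the form of the normality check are details that an analyst would settle sensibly when producing the tables.

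What remains is a presentational weakness confined to skewed data. At 15 per arm and a 0.8 SD shift, about a quarter of significant Kruskal-Wallis results would stand beside means and SDs that do not show the difference, rising to 47% under the least favourable form of the check. That affects how the result reads, not whether the test is valid.

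The textual finding is certain. The sizes rest on assumed arm sizes, distributions and shifts, none of which the document states.

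### For mm parameters the three-arm test uses no covariate; where a pre-graft value is already on record, ANCOVA on it is a cheap gain in efficiency.

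*Combined protocol and SAP*

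**What the plan says.** The analysis section describes outcomes as "continuous variables, such as linear measurements measured in mm". On the choice of test it says "The normality will be assessed by means of a Kolmogorov-Smirnov test", and that ANOVA or Kruskal-Wallis "with post-hoc analysis will be used to compare between three groups". No covariate is named there.

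ANCOVA appears in the next sentence, as an alternative to simple linear regression: "analysis of covariance test will be employed to analyze the factors independently associated with peri-implant parameters". That sentence names neither the randomised arm as factor nor any pre-graft value as covariate.

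On timing, Methods gives one visit: "Participants have a 6-month follow-up visit after placement of the dental implant". The Official Title reads "Ultrasound-based Imaging to Detect Early Changes of Hard and Soft Tissue Around Immediately Placed Implants", which suggests an earlier reading but does not say what it is or when it is taken. Methods also says that "consented subjects underwent immediate implant placement and were randomized to either 2 groups of soft tissue grafting", or to no graft. The Objective concerns a different outcome, implant "survival rate over a period of 6 months".

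**The concern.** Tissue dimensions at 6 months may well depend on the dimensions the patient started with. If a starting value is on record, leaving it out of the arm comparison keeps between-patient variation in the error term that could be removed at almost no cost.

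The plan also leaves open which unadjusted comparison is meant. A test of 6-month values and a test of changes both fit the text, and which has more power depends on quantities the document does not give. ANCOVA on the pre-graft value removes the need to guess. At stake are power and the width of confidence intervals for the mm parameters, not the validity of the result.

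**Working it through.** **Inputs.** From the document: three arms, two-sided 0.05, ANOVA or Kruskal-Wallis after a Kolmogorov-Smirnov test. Sample size, effect size, SDs and the pre/post correlation are not given, so there is no planned figure to reproduce. Assumed: equal arms of n = 10 to 30; true means 0, 0.8, 0.8 in units of the 6-month SD; r = correlation of pre-graft and 6-month values; k = pre-graft SD / 6-month SD.

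**Variance, relative to 6-month values (= 1).**
- Change: 1 + k² − 2rk, so changes beat 6-month values only if r > k/2.
- ANCOVA: 1 − r², which is 0.91, 0.75, 0.51 at r = 0.3, 0.5, 0.7.
- ANCOVA relative to change: (1 − r²)/(1 + k² − 2rk). Denominator minus numerator is (r − k)², so the ratio is never above 1 and equals 1 only at r = k.

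| Ratio ANCOVA/change | r = 0 | 0.3 | 0.5 | 0.7 |
|---|---|---|---|---|
| k = 0.7 | 0.67 | 0.85 | 0.95 | 1.00 |
| k = 1 | 0.50 | 0.65 | 0.75 | 0.85 |
| k = 1.3 | 0.37 | 0.48 | 0.54 | 0.59 |

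For k below 1 the gain grows as r moves away from k on either side: at k = 0.7 the ratio is 0.67 at r = 0, 1.00 at r = 0.7 and 0.61 at r = 0.95. For k above 1, r cannot reach k. The ratio then peaks at r = 1/k, where it equals 1/k² (k = 1.3: 1/1.69 = 0.59 at r = 0.77).

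**Power, normal data (noncentral F).** Σ(μ − mean)² = 0.8² × 2/3 = 0.427. At n = 15 the noncentrality for 6-month values is 15 × 0.427 = 6.40, with df 2 and 42. For ANCOVA it is 6.40/(1 − r²), divided by 1 + 1/(3n − 5) = 1.025 for a random covariate, with df 2 and 41. That is 6.24, 6.86, 8.33, 12.24 at r = 0, 0.3, 0.5, 0.7.

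| Power, 15 per arm | r = 0 | 0.3 | 0.5 | 0.7 |
|---|---|---|---|---|
| 6-month values | 58% | 58% | 58% | 58% |
| Changes, k = 1 | 32% | 44% | 58% | 81% |
| Changes, k = 0.7 | 42% | 55% | 69% | 87% |
| ANCOVA | 57% | 61% | 70% | 86% |

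At r = 0 the cost of ANCOVA against 6-month values is 1.5, 1.2, 0.9, 0.4 points at 10, 15, 20, 30 per arm. It breaks even at |r| = 0.21, 0.16, 0.14, 0.11.

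**Power, skewed data (simulation).** Lognormal, sigma 0.75, scaled to SD 1, 15 per arm, k = 1, r on the log scale.

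| Power | r = 0 | 0.3 | 0.5 | 0.7 |
|---|---|---|---|---|
| Kruskal-Wallis, 6-month values | 85% | 85% | 85% | 85% |
| Kruskal-Wallis, changes | 50% | 66% | 78% | 93% |
| Ordinary ANCOVA | 64% | 68% | 73% | 84% |
| Rank-based ANCOVA | 85% | 88% | 92% | 97% |

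So ordinary ANCOVA is not a safe replacement for Kruskal-Wallis, whereas the rank-based version is.

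**With the normality switch** (Kolmogorov-Smirnov on residuals, r = 0.5, k = 1, 15 per arm), power for values / changes / ANCOVA route is 59/59/71% for normal, 85/75/91% for skewed and 79/78/86% for heavy-tailed data. Null rejection was 0.046 to 0.056 for the unadjusted routes and 0.048 to 0.057 for the ANCOVA route.

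**Where ANCOVA loses.** At r = k = 0.7 the switched ANCOVA route is below changes: normal data 66.3 against 68.4% (n = 10) and 86.3 against 87.4% (n = 15); heavy-tailed 81.1 against 83.8% and 94.7 against 95.9%. A heavy-tailed run at r = k = 0.9, 15 per arm, means 0, 0.4, 0.4, gave 83 against 87%.

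**The case against.** **The covariate may not exist.** The document mentions no pre-graft mm measurement. Placement and grafting follow extraction closely, so a peri-implant dimension could be taken before grafting only in the interval after placement. The change in the title could equally run from a reading taken after surgery, which must not be a covariate because the graft can already have altered it. This stands in full, and the recommendation is therefore conditional.

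**ANCOVA is already named.** It is, and randomised arm is a natural factor for it. But the sentence is about associated factors, while the sentence that compares the three groups names other tests. The text is ambiguous on whether arm is covered; it does not assign ANCOVA to the arm comparison.

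**The figures describe no particular trial.** Correct. They show direction and rough size over assumed ranges, and the largest loss against change scores depends on the cases tried.

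**It may be too late.** The document is dated 10/14/2024 and reports placement and randomisation in the past tense. Whether arm-level results have been seen is not stated.

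A reader might infer that the unadjusted comparison is biased or invalid, or that the investigators hold baseline values and ignore them. The document supports neither: randomisation protects the unadjusted tests, and no baseline value is described.

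**Conclusion.** This is a cheap improvement in efficiency, limited to mm parameters that have a pre-graft value on record. It is not an error, and it leaves the implant-survival objective untouched.

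Under the assumed r and k, adjustment removes 9% to 49% of the variance of 6-month values for r from 0.3 to 0.7, and never has a larger large-sample variance than change scores. At 15 per arm with normal data that takes power from 58% to between 61% and 86%. Against this stand about 1 point of power if r is near 0 (0.4 to 1.5 points at 30 to 10 per arm), and a few points against changes when r is close to k in small samples.

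The textual part is firm: no covariate is named and the compared quantity is not stated. The size of the gain is not, because sample size, r, k, effect size and distribution are all assumed. If no pre-graft value exists, what remains is a request to state the compared quantity.

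**What to change.** Add to the Statistical Analysis Plan:

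- For each mm parameter with a value already recorded before grafting, compare arms at 6 months by ANCOVA with randomised arm as factor and that value as covariate. Report the overall arm test and the adjusted pairwise differences with 95% CIs.
- If the residuals are judged non-normal, use a rank-based ANCOVA for the overall test: regress 6-month ranks on pre-graft ranks and compare the residuals across arms. Apply the same rank-residual comparison pairwise, with the multiplicity adjustment used for the planned post-hoc tests. The plan does not name that adjustment, so name it here.
- Do not use values measured after grafting as covariates.
- For parameters without a pre-graft value, keep ANOVA or Kruskal-Wallis and state for each whether the 6-month value or a change from a named earlier measurement is compared.
- Say whether the existing ANCOVA sentence covers arm or only other, exploratory factors.
- Date the change before arm-level results are seen. If they have been seen, say so and label the adjusted analysis post hoc.

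The cost is SAP wording and one degree of freedom, with the small power risks given above. No new measurement is needed.

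### The factor analysis may be run as one-predictor regression, which cannot show that a factor is independently associated with an outcome

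*Combined protocol and SAP*

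**What the plan says.** The Statistical Analysis Plan gives the factor analysis one sentence: "Simple linear regression (univariate) analysis or analysis of covariance test will be employed to analyze the factors independently associated with peri-implant parameters".

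The plan does not say when each method applies. It names no candidate factors, no ANCOVA covariates and no particular peri-implant parameter as the outcome, and it describes no multivariable step to follow the simple regressions.

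The comparison of the randomised groups is planned separately: "The analysis of variance test or the Kruskal-Wallis's test with post-hoc analysis will be used to compare between three groups". The only assumption check is on distribution: "The normality will be assessed by means of a Kolmogorov-Smirnov test".

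**The concern.** To call a factor independently associated with an outcome is to say that the association remains after other factors are allowed for. A one-predictor regression allows for none, so the method named first cannot deliver the stated aim. This follows from the definition and needs no assumption about the trial.

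Three things together would do harm: the univariate option is chosen; a factor with no effect of its own is correlated with something that does drive the outcome; and the crude result is reported in the plan's own word. The plan permits the first and supplies the third. Whether the second holds is unknown. Readers would then take a crude association, possibly a stand-in for another factor, as an adjusted one.

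**Working it through.** **1. Can anything in the plan select the method?** The normality check is the only candidate. Simple regression and ANCOVA are both linear models with normal errors, so a Kolmogorov-Smirnov result would not separate them. Nothing else in the document bears on the choice.

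**2. Inputs.** From the document: three randomised groups and a two-tailed 0.05 level. Assumed, because the document gives no values: total N (45, with 30 and 60 as alternatives), the correlations, the strength of the driver and its measurement reliability. The plan has no figure of its own to reproduce.

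**3. What the crude slope estimates.** Let all variables have unit variance. A driver x1 has correlation b with outcome y. A second factor x2 has correlation ρ with x1 and no effect of its own. Then:

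- expected slope of y on x2 alone = ρ × b
- expected slope of y on x2, given x1 = 0

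For b = 0.3 and ρ = 0.3, 0.5, 0.7 the crude slope is 0.09, 0.15, 0.21. For b = 0.6 it is 0.18, 0.30, 0.42.

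**4. How often x2 is flagged.** Each setting was simulated 20,000 times with three equal arms. The adjusted model contains two arm indicators, x1, x2 and two unrelated factors. In the third column x1 is replaced by an unrelated factor. In the fourth, x1 is measured with reliability 0.7. Entries are percentages for ρ = 0.3/0.5/0.7 at N = 45.

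| b | Simple regression | Adjusted, driver listed | Adjusted, driver omitted | Adjusted, driver at reliability 0.7 |
|---|---|---|---|---|
| 0.3 | 9/17/29 | about 5 | 8/15/26 | 5/6/8 |
| 0.45 | 14/32/58 | about 5 | 13/29/52 | 6/8/12 |
| 0.6 | 22/52/84 | about 5 | 20/48/79 | 7/10/20 |

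The second column ranges from 4.6 to 5.2%. At ρ = 0 simple regression also gives about 5%.

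**5. Closed-form check.** By Fisher's z, the rejection rate for a true correlation r is about Φ(z − 1.96) + Φ(−z − 1.96), with z = atanh(r) × √(N − 3). For N = 45 and r = 0.5 × 0.3 = 0.15, z = 0.1511 × 6.481 = 0.98, which gives 16.5% (simulated 16.7%). For r = 0.5 × 0.6 = 0.30, z = 2.01, which gives 51.8% (simulated 52.4%).

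**6. Other sample sizes.** Ranges are over ρ = 0.3 to 0.7.

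| N | b | Simple regression | Adjusted, driver omitted |
|---|---|---|---|
| 30 | 0.3 | 8–20% | 7–17% |
| 30 | 0.6 | 16–66% | 14–57% |
| 60 | 0.3 | about 10–37% | 10–35% |
| 60 | 0.6 | 28–92% | 26–90% |

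**7. Why mismeasurement leaves a residue.** With driver reliability R, the expected adjusted slope of x2 is ρb(1 − R)/(1 − ρ²R). For ρ = 0.7, b = 0.6, R = 0.7 this is 0.42 × 0.30/0.657 = 0.19, against 0.42 unadjusted.

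**The case against.** ANCOVA stands in the same sentence and can support the claim, so the plan can be followed correctly. The *or* may be shorthand for two situations (one continuous predictor, or a group factor with covariates), and *independently* may loosely mean that each factor is examined separately. The percentages rest wholly on assumed inputs. Adjustment may not cure the problem either: with the driver omitted, the adjusted model does little better than simple regression. It also costs power, and deleting one word achieves the match between wording and method.

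Much of this stands, as a limit. The figures show a mechanism and not a size for this trial. The adjusted model protects only as far as the real drivers are listed and well measured. If the factor is the randomised arm, a crude estimate is not confounded in expectation, so the point concerns non-randomised factors only.

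The alternative readings do not rescue the sentence. Neither is stated, and the second is not the usual meaning of the phrase. As written, simple regression alone is sufficient under the plan.

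**Conclusion.** The concern holds and should be corrected. The plan names, as sufficient for finding independently associated factors, a method that yields only unadjusted associations, and nothing elsewhere in the document repairs this. The textual point is certain.

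The numerical consequence is not known. It is nil if the factors are uncorrelated, and it grows with the correlation, the driver's strength and the sample size. In the assumed settings with correlated factors at N = 45, simple regression gives false flags in 9 to 84% of trials, against about 5% with the driver in the model and measured without error.

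The effect is confined to the factor analysis. The randomised three-group comparison and the stated objective, on implant survival over 6 months, are untouched.

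**What to change.** **Preferred.** Replace the sentence with: *Factors associated with each continuous peri-implant parameter will be assessed in one multivariable linear model (ANCOVA) containing randomised arm, a short list of factors fixed before analysis that includes the expected main determinants, and, where measured, the baseline value of the parameter. Adjusted coefficients with 95% confidence intervals will be reported and described as independent of the listed factors only. Simple regressions will be labelled unadjusted and not described as independent.* The investigators must write the factor list into the plan before analysis. Categorical outcomes such as implant survival fall outside this sentence.

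**Minimum.** If no multivariable model is wanted, delete *independently* and label the simple regressions unadjusted. This costs no power.

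**Cost of the preferred fix.** It takes two sentences, an agreed list and minor programming in the same software, plus some precision:

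- Parameters: intercept 1 + arm 2 + four factors 4 = 7, leaving 45 − 7 = 38 residual degrees of freedom, or 30 − 7 = 23. A separate baseline term leaves 37 or 22. Simple regression leaves 43 or 28.
- Standard error: adjusting for a factor correlated ρ multiplies it by 1/√(1 − ρ²), which is about 1.05, 1.15 and 1.40 at ρ = 0.3, 0.5 and 0.7, before any gain from explained variance.
- Power for a real driver (b = 0.3, N = 45): 53% in simple regression; 48/44/38/28% adjusted at ρ = 0/0.3/0.5/0.7, or 47/43/37/27% with a baseline term that explains nothing. At N = 30: 37%, against 31/29/25/18%.

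The list must therefore be short, but leaving out a main driver brings the error back.
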